6.8.3 Multiplicity considerations

No multiplicity issues are expected as the analysis will be mainly descriptive.

6.8.4 Other efficacy analysis

NA.

6.9 Safety Analysis

Safety will be evaluated in the Safety Population.

Adverse events and safety evaluations occurring during the four analysis periods (see section 6.1 for reference) will be analyzed. During the Follow-Up period only, adverse events categorized as PML will be collected.

6.9.1 Adverse Events

Treatment-emergent adverse events are adverse events that developed or worsened during the treatment-emergent adverse event period (from first date of IMP until last date of IMP +70 days).

The primary focus of adverse event reporting will be on treatment-emergent adverse events. Post-treatment PML events will be described in a separate table, as well as pre-treatment, treatment emergent and post-treatment deaths.

Adverse events will be considered only in the period in which it starts.

The following summaries will be generated for the safety population.

- a. Overview of adverse events during all study and by analysis period, summarizing number (%) of patients with any
 - Adverse event
 - Treatment-emergent adverse event
 - Serious treatment-emergent adverse event
 - Non-serious treatment-emergent adverse event
 - Treatment-emergent adverse event leading to death
 - Treatment-emergent adverse event leading to permanent treatment discontinuation
 - Treatment-emergent adverse event related to study drug
- b. All adverse events during all study by primary SOC and PT, showing number (n) and percentage (%) of patients with at least 1 adverse event sorted by the SOC internationally agreed order. The other level (PT) will be presented in alphabetical order
- c. All treatment-emergent adverse events by analysis period and by primary SOC and PT, showing number (n) and percentage (%) of patients with at least 1 treatment-emergent adverse event sorted by the SOC internationally agreed order. The other level (PT) will be presented in alphabetical order

- d. All treatment-emergent adverse events related to IMP by analysis period and by primary SOC and PT, showing the number (n) and percentage (%) of patients with at least 1 treatment-emergent adverse event, sorted by the internationally agreed SOC order. The other level (PT) will be presented in alphabetical order
- e. All treatment-emergent adverse events by analysis period and by maximal severity, presented by primary SOC and PT, showing the number (n) and percentage (%) of patients with at least 1 treatment-emergent adverse event by severity (i.e., mild, moderate, or severe), sorted by the sorting order defined above.
- f. All treatment-emergent serious adverse events by analysis period and by primary SOC and PT, showing the number (n) and percentage (%) of patients with at least 1 serious treatment-emergent adverse event, sorted by the internationally agreed SOC order.
- g. All treatment-emergent non-serious adverse events by analysis period and by primary SOC and PT, showing the number (n) and percentage (%) of patients with at least 1 serious treatment-emergent adverse event, sorted by the internationally agreed SOC order.
- h. All treatment-emergent serious adverse events related to IMP by analysis period and by primary SOC and PT, showing the number (n) and percentage (%) of patients with at least 1 treatment-emergent serious adverse event, sorted by the internationally agreed SOC order. The other level (PT) will be presented in alphabetical order.
- i. All treatment-emergent non-serious adverse events related to IMP by analysis period and by primary SOC and PT, showing the number (n) and percentage (%) of patients with at least 1 treatment-emergent serious adverse event, sorted by the internationally agreed SOC order. The other level (PT) will be presented in alphabetical order.
- j. All treatment-emergent adverse events leading to treatment discontinuation by analysis period and by primary SOC and PT, showing the number (n) and percentage (%) of patients sorted by the internationally agreed SOC order. The other level (PT) will be presented in alphabetical order. Information will be presented in two columns separately for all and related TEAEs leading to treatment discontinuation.
- k. All treatment-emergent adverse events leading to death by analysis period and by primary SOC and PT, showing the number (n) and percentage (%) of patients sorted by the internationally agreed SOC order. Information will be presented in two columns separately for all and related TEAEs leading to death.

- I. Number (n) and percentage (%) of patients who died by study period (pre-treatment, treatment-emergent, post-treatment).
- m. All PML events during follow up by primary SOC and PT, showing number (n) and percentage (%) of patients with at least 1 one PML event sorted by the SOC internationally agreed order. The other level (PT) will be presented in alphabetical order

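### SAP 6.9.1 items g and i are headed as non-serious adverse event tables but define their counts as patients with a serious event

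*SAP*

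**What the plan says.** SAP section 6.9.1 (Adverse Events) lists the safety summaries as items a to m. Four of them split treatment-emergent events by seriousness:

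- Item f is the serious-event table: "All treatment-emergent serious adverse events by analysis period and by primary SOC and PT".
- Item g is the non-serious table: "All treatment-emergent non-serious adverse events by analysis period and by primary SOC and PT". Its counting rule, however, reads "by primary SOC and PT, showing the number (n) and percentage (%) of patients with at least 1 serious treatment-emergent adverse event".
- Item h is the IMP-related version of f.
- Item i is the IMP-related version of g: "All treatment-emergent non-serious adverse events related to IMP by analysis period and by primary SOC and PT". Its counted unit is "patients with at least 1 treatment-emergent serious adverse event, sorted by the internationally agreed SOC order. The other level (PT) will be presented in alphabetical" (quote cut short).

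Overview item a has separate patient counts for serious events and for the category "Non-serious treatment-emergent adverse event". The overview and items f to i are all produced by analysis period, and section 6.1 defines four such periods. Items c, d and e tabulate by SOC and PT, respectively, all treatment-emergent events, those related to IMP, and events by maximal severity.

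Protocol section 9.7.1.8.2 asks for treatment-emergent events by SOC and PT, by highest severity and by causal relationship. It does not ask for a split by seriousness.

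**The concern.** In g and i the heading and the counting rule pick out different patients. The heading says the table is about non-serious events; the rule admits a patient because of a serious one. The wording matches f and h so closely that it looks carried over from them.

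The SAP is the document against which tables are programmed and checked. Here it gives two incompatible instructions for the same cell. A programmer who follows the rule produces a table that contradicts its own title and the overview. One who follows the title produces a sensible table that does not match the written plan. Safety at 12 weeks is part of the primary objective, and protocol section 9.7.2 puts enrolment at 25 subjects, so losing even a few patients from a count would be visible.

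**Working it through.** No figure in the plan needs reproducing, and no formula applies. The check compares the heading with the counting rule in each item.

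| Item | Events named in the heading | Patients admitted by the counting rule | Compatible? |
|---|---|---|---|
| c | all treatment-emergent | at least one treatment-emergent event | yes |
| d | related to IMP | at least one treatment-emergent event (relatedness not repeated) | yes, if the heading selects the events |
| e | by maximal severity | at least one treatment-emergent event, by severity | yes |
| f | serious | at least one serious event | yes |
| g | non-serious | at least one **serious** event | **no** |
| h | serious, related to IMP | at least one serious event (relatedness not repeated) | yes, if the heading selects the events |
| i | non-serious, related to IMP | at least one **serious** event | **no** |

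Items b and m are also compatible. Items j, k and l have no rule of the at-least-one kind. The quoted rule in g also stands in f, where it is correct; the error lies in pairing it with a non-serious heading.

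To see what each reading does, take three hypothetical patients: A has only non-serious events, B has only serious events, and C has both.

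1. *The counting rule alone governs g.* B and C are counted and A is not. This is table f again.
2. *The heading selects the events and the rule selects the patients.* Only C is counted, so g shows non-serious events only in patients who also had a serious one.
3. *The heading governs and the word serious is ignored.* A and C are counted. This is the only reading that agrees with the non-serious line of overview a, which also counts A and C.

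Readings 1 and 2 both leave out A. The same holds in item i for a patient whose related events were all non-serious.

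The example also shows which cross-check is valid. Table f counts B and C (2 patients), and a correct g counts A and C (2 patients). Adding them gives 2 + 2 = 4, but only 3 patients had any event, because C is in both. So f and g can each be matched to their own line in overview a, but their sum need not equal any line. For h and i there is no matching line: overview a has one line for events related to study drug and does not divide it by seriousness.

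Neither the protocol nor the rest of the SAP restates or corrects the rule for g or i.

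**The case against.** The strongest reply is that the intent is plain and nobody would be misled. The headings say non-serious, and overview a keeps the two categories apart. The counting phrases are loose elsewhere too: those in d and h do not repeat relatedness, which suggests template text with the heading meant to select the events. This has force. It means the wrong table appears only if the rule is followed literally, and a careful programmer may well produce the right one. But the two cases differ. In d and h the rule leaves out a qualifier that the heading supplies; in g and i it states the opposite of the heading. Following the heading there means overriding the plan.

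The second reply is that little depends on g and i. The protocol does not require a split by seriousness, and c, d and e meet what it does require. This stands in full, and it limits the point.

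A reader might go further and infer that E6011's common adverse events would be under-reported by arm. The documents do not support that. Item c tabulates every treatment-emergent event by SOC and PT with a correct rule, d does so for related events and e by severity, so common events remain in the safety report.

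A reader might also want to size the loss from Study 101, where 18 of 28 subjects (64.3%) had an adverse event in 12 weeks. With 25 / 2 = 12.5 patients per arm, 0.643 × 12.5 is about 8 per arm with any event. That is not a measure of this error. The rate comes from an open-label study without placebo that pooled four dose groups, an equal split of the 25 is assumed, and above all the documents give no serious-event rate. The number of patients g would lose therefore cannot be derived.

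**Conclusion.** The counting rules in items g and i are wrong as written. If they are followed, each table leaves out every patient whose relevant events were all non-serious, and g disagrees with the non-serious line of overview a whenever such a patient exists. The error recurs in each analysis period for which the tables are produced.

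The conclusion about direction rests only on the SAP text. The size depends on how many patients have non-serious events and no serious one, which the documents do not allow anyone to estimate. The damage is confined to two supplementary descriptive tables. The all-event, related-event and severity tables and the efficacy analysis are unaffected. It is a small internal inconsistency in the operative analysis section, worth correcting because the correction is so cheap.

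**What to change.** - In item g, count *patients with at least 1 non-serious treatment-emergent adverse event*.
- In item i, count *patients with at least 1 treatment-emergent non-serious adverse event related to IMP*.
- As a programming check, match the any-event row of f to the serious line of overview a, and the any-event row of g to the non-serious line, within the same analysis period. Do not add f and g, or h and i, because a patient can have both kinds of event. Do not look for an overview line for h or i, because there is none.
- Optionally, repeat relatedness in the counting phrases of d and h in the same edit, so that heading and rule agree throughout the list.

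The cost is a few words in SAP 6.9.1. The table shells are not part of the documents reviewed; if they carry the same wording, they need the same edit. No data collection, sample size or other analysis changes.

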6.9.2 Laboratory

Laboratory parameters will be descriptively summarized by treatment and time point, see Table 2 for further reference.

Table 2 Laboratory Parameters

Category	Items
Haematology testing	White blood cell count (Leukocytes), red blood cell count (Erythrocytes), hemoglobin, hematocrit, platelet count, differential white blood cell count (neutrophils, lymphocytes, monocytes, eosinophils, basophils)
Blood biochemistry testing	
Liver function tests	Total bilirubin, ALP, AST, ALT, g GTP
Renal function tests	BUN, creatinine
Other tests	Plasma glucose, serum glucose, albumin, total cholesterol, triglyceride, amylase, inorganic phosphate, LDH, CK, total protein, uric acid, Na, K, Cl, Ca, CRP
Urinalysis	pH, protein, glucose, urobilinogen, ketone bodies, occult blood, specific gravity, amylase (U/g creat), amylase (U/L)

Summary statistics for continuous variables are to be calculated for measurements at each Visit and their change from baseline by treatment group. For sequential categorical variables, laboratory values are to be categorized into under normal range (L), within normal range (N), or over normal range (H). Then, the number of subjects and percentage by LNH categories are presented in a shift table (baseline vs each visit post-dose). In addition, post-dose maximum and minimum values are to be similarly presented at each visit.

In case that the total cell count of neutrophils, lymphocytes, monocytes, eosinophils, basophils is not given, and the percentage of them to the total white blood cell count is given, the total cell count of them can be derived as:

$$\text{Total cell count of a specific white cell} = \frac{\text{Percentage of a specific white cell}}{100} * \text{Total WBC}$$

In case that the percentage of cell count of neutrophils, lymphocytes, monocytes, eosinophils, basophils relative to total white cell count is not given, and the total count of them is given, the percentage of a specific white cell can be derived as:

$$\text{Percentage of a specific white cell} = \frac{\text{Total cell count of a specific white cell}}{\text{Total WBC}} * 100$$

6.9.3 Vital signs

Blood pressure (systolic, diastolic: mmHg), pulse rate (bpm), temperature (°C), height (cm), and weight (kg) will be descriptively summarized by treatment and visit in the three analysis periods (see section 5.1 for further reference)

6.9.4 Standard 12-lead ECG examinations, neurological symptoms

Percentage of patients with any clinical finding (abnormal) along the first 12 weeks will be descriptively summarized by treatment group.

6.9.5 Blood CD4 positive cell count.

The number of CD4 (U/µL) will be summarized descriptively as quantitative variable by treatment and time point.

6.10 Other Analyses

6.10.1 Pharmacokinetic data handling

Lower Limit of Quantification (LLOQ) of Serum E6011 Concentration

The LLOQ of serum E6011 concentration is 0.1 µg/mL.

BLQ Handling for Calculation of PK Parameters

Not Applicable.

BLQ Handling for Developing Concentration–Time Profiles

When developing individual concentration–time profiles, BLQ values are replaced with

- a. zero for time points prior to the first non–zero concentration following first dosing in a linear plot
- b. “missing” for time points after the first non–zero concentration following first dosing in a linear plot
- c. “missing” for all BLQ values in a semi–logarithmic plot.

When calculating the mean (or median) value for the concentration at a given time point, all BLQ values will be assigned as zero. If the proportion of values reported as BLQ is more than 50% or the calculated mean (or median) value is less than LLOQ at a time point, the value of mean (or median) is treated as:

- a. zero for time points prior to the first non-zero mean (or median) concentration following first dosing in a linear plot
- b. "missing" for time points after the first non-zero mean (or median) concentration following first dosing in a linear plot
- c. "missing" for all BLQ values in a semi-logarithmic plot.

BLQ Handling for Developing Tables

BLQs are handled with same manner as the one in a linear plot for mean or median concentration profiles (see section 16.2.3)

Handling of anomalous concentration values

Anomalous values are those that are inconsistent with known or expected PK behavior of the drug, but are not defined on the basis of statistical tests for outliers. Individual concentrations deemed to be anomalous can be excluded from the PK analysis and median and mean profiles; such anomalous values will be identified in the report. Clear justification must be provided in the report for exclusion of any data.

General rules for presentation of drug concentrations and PK parameters

To show the presentation of individual/raw (raw, hereafter) values and summary statistics, the following rule should be applied: for drug concentrations, all of summary statistics (mean, median, and standard deviation (SD), raw minimum and maximum) have 3 significant digits.

Typical Variable	Standard Unit	N	Digit rule	Raw Minimum Maximum	Mean Median	SD
E6011 concentration	µg/mL	x	Significant digits	3	3	3

6.10.2 Pharmacokinetic Parameters

Serum concentrations of E6011 will be summarized using the pharmacokinetic analysis set. Summary statistics for serum E6011 concentrations are to be calculated for each specified sampling timepoint and treatment group.

Serum E6011 concentration-time profiles are also to be created.

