4.8 Pharmacokinetic Parameters endpoints

Individual serum concentration values of E6011 will be summarized as follows:

- Pharmacokinetics and serum E6011 concentration
 - Individual serum concentration values of E6011 will be listed and summarized using descriptive statistics (n, mean, standard deviation, geometric mean, CV, geometric CV, median, Q1, Q3, minimum and maximum) and nominal time point. The data of time points in subject with interruption will not be included on calculation of summary statistics after the interruption.
 - Actual sampling time and serum concentrations of E6011 for each subject will be listed.
 - The individual serum E6011 concentration–time profile will be displayed in linear and semi–log scales using actual sampling times in the same graph.
 - The mean serum concentrations of E6011 will be displayed using nominal blood sampling times with standard deviation in linear and semi–log scales in the same graph.

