- 2) Rescue Period (Open label): comprises from week 12 to week 24 for non-responders. Subjects with a reduction in the CDAI of less than 70 compared to baseline after finishing evaluation in Week 12 of the remission-induction period are to move on to the rescue period. The rescue period is to last 12 weeks, with 10 mg/kg of E6011 administered in an unblinded manner on Week 12, Week 13, Week 14 and every two subsequent weeks until Week 22.
- 3) Extension Period (Open label): comprises from week 12 to week 52 for responders at week 12 and from week 24 to week 64 for non-responders at week 12. Subjects who

finished evaluation at Week 12 of the remission-induction period and had a CDAI response of 70 or more, and subjects who moved on to the rescue period and finished evaluation at Week 24 with a CDAI response of 70 or more are to move on to their respective extension period. The extension period is to last 40 weeks, with 10 mg/kg E6011 administered in an unblinded manner every four weeks up to Week 48(responders) or Week 60(non-responders).

- 4) Post-Observation Period: After the extension period of the clinical trial has been finished or discontinued, examinations are to be carried out 28 days after the completion or discontinuation of the extension period and 70 days after the last administration of the IMP.
- 5) Follow-up Period: PML onset is to be investigated over the phone, etc. every 6 months in the two-year follow-up period after the last IMP administration.

Four analysis periods are defined:

- 1) Remission-induction period: as defined above.
- 2) Rescue period: as defined above. This period will be used only for adverse events endpoints.
- 3) Entire administration period comprises the remission-induction period, the rescue period, the extension period and the post-observation period as defined above.
- 4) Follow-up period: as defined above.

Analyses of the remission-induction period will be performed after the remission-induction period is completed. Analyses of the entire administration period (remission-induction period, rescue period, extension period and post-observation period) will be performed after the post-observation period is completed. Analysis of the follow-up period will be performed after the follow-up period is completed.

In all TFLs that are displayed by treatment groups they will refer to the remission-induction treatments.

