6.6.1 Pharmacokinetic Sampling

Blood samples for the determination of serum E6011 concentrations are to be collected pre-dose and post the end of the infusion (within 10 minutes of the end of the infusion from week 0 to week 10).

Blood samples will be collected as follows;

For all subjects during the remission-induction period blood samples will be collected during weeks 0, 1, 2, 4, 6, 8, 10, 12 and upon discontinuation.

During the extension period (responders) blood samples will be collected during weeks 16, 20, 24, 28, 32, 36, 40, 44, 48, 52 and upon discontinuation.

During the rescue period (non-responders) blood samples will be collected during weeks 13, 14, 16, 18, 20, 22, 24 and upon discontinuation.

During the extension period (non-responders) blood samples will be collected during weeks 28, 32, 36, 40, 44, 48, 52, 56, 60, 64 and upon discontinuation.

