6.10.5 PK-PD Relationships

PK-PD relationships will be explored graphically, the geometric mean serum E6011 concentration time profile and PD biomarker time profile will be displayed in the same graph on linear and semi log scales by dose. These plots will be generated by race (all patients, and by Japanese and non-Japanese patients).

Different endpoints and the corresponding PD biomarker will be displayed as a scatter plot and correlation coefficients should be calculated:

- E6011 concentrations
- CDAI
- PRO2
- SES-CD

These plots will be generated by race (all patients, and by Japanese and non-Japanese patients).

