10 GENERAL FORMAT OF TABLES, FIGURES AND SUBJECT DATA

Tables and listings will be produced in accordance with the principles outlined by the ICH E3 guideline. All summary tables will be presented by treatment group and race (all, Japanese and non-Japanese).

The design of the tables will be clear and concise so that comparative reading is easily possible.

All descriptive variables will be tabulated. Quantitative variables will be described showing their number of available and missing observations, mean and its CI (95% level), median, standard deviation, the range (minimum and maximum) and the first and third quartiles. Frequency and percentage will describe qualitative variables.

Missing values will be tabulated with their frequency but will not be included in the calculation of percentages. Analysis will be based on observed cases, i.e., no replacement of missing data is planned in general except otherwise planned in the appropriate statistical methodology section (section 11, section 12 or 14).

Pharmacokinetic data (E6011 serum concentrations) will be summarized by treatment group and race (All, Japanese and Non-Japanese) and evaluation time, including the number of sample results, minimum, medium, maximum, mean, standard deviation and coefficient of variation (CV). In addition, geometric means and geometric CV will be also shown.

Serum E6011 concentration vs time curves will be prepared. A serum concentration profile will be prepared for each subject and shown individually on a single plot per patient. A plot showing all serum profiles generated per treatment group will be prepared.

Summary serum E6011 concentration vs time profiles will also be prepared. A geometric mean serum profile will be shown by treatment group individually and grouped by treatment.

Pharmacodynamic data (serum total FKN concentrations, faecal calprotectin and serum CRP concentration measured values, change and % change from baseline) will be summarized by treatment group, evaluation time and race (all, Japanese and non-Japanese), including the number of sample results, minimum, medium, maximum, mean, standard deviation and coefficient of variation (CV). In addition, geometric means and geometric CV will be also shown.

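### E6011 concentration summaries at Weeks 16, 20 and 24 pool 14-day rescue troughs with 28-day extension troughs within each induction arm

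*SAP*

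**What the plan says.** SAP 6.10.2: "Summary statistics for serum E6011 concentrations are to be calculated for each specified sampling timepoint and treatment group". SAP 10 adds race: "Pharmacokinetic data (E6011 serum concentrations) will be summarized by treatment group and race (All, Japanese and Non-Japanese) and evaluation time". SAP 4.8 puts the mean profiles on nominal time: "The mean serum concentrations of E6011 will be displayed using nominal blood sampling times with standard deviation".

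SAP 6.1 settles what treatment group means after Week 12: "In all TFLs that are displayed by treatment groups they will refer to the remission-induction treatments". The same section lists rescue as an analysis period but restricts it: "This period will be used only for adverse events endpoints". Protocol 9.7.1.10 repeats the induction pharmacokinetic analysis for the entire dosing period.

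Both paths are sampled at Weeks 16, 20 and 24. SAP 6.6.1 says for rescue: "During the rescue period (non-responders) blood samples will be collected during weeks 13, 14, 16, 18, 20, 22, 24 and upon discontinuation"; and for extension: "During the extension period (responders) blood samples will be collected during weeks 16, 20, 24, 28, 32, 36, 40, 44, 48, 52". The visit-window table in SAP 6.6 gives each of these weeks a single window for everyone.

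The introduction to SAP section 6 says that the pharmacokinetic objectives are left to a separate analysis plan.

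**The concern.** At Week 12 each arm divides by CDAI response. Responders go on to E6011 every four weeks. Non-responders are dosed at Weeks 12, 13 and 14 and then every two weeks to Week 22 (protocol 9.4.1). Arm, race and nominal week do not tell these two schedules apart, so a mean at Week 16, 20 or 24 depends on how many patients in the arm responded and need not describe exposure under either schedule. The SD is affected too, because it takes in the gap between the paths.

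Pharmacokinetics is a stated secondary objective. SAP 6.10.5 also builds on these values: "the geometric mean serum E6011 concentration time profile and PD biomarker time profile will be displayed in the same graph". Because path is set by CDAI response, a plot pooling later concentrations with calprotectin or CRP could show an association that the dosing rule created.

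**Working it through.** The documents state no trough ratio, so there is no figure of theirs to reproduce on this point.

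**Inputs**
- Induction doses: Weeks 0, 1, 2, 4, 6, 8, 10 (E6011 arm only). Rescue doses: Weeks 12, 13, 14, 16, 18, 20, 22. Extension doses for responders: Weeks 12, 16, 20 and so on. All E6011 doses are 10 mg/kg (protocol 9.4.1).
- Samples after Week 12 are pre-dose. Post-infusion samples are taken only from Week 0 to Week 10 (protocol Table 4, note g).
- Half-life: protocol 9.2 equates 70 days with about five of the longest observed half-lives, so 70/5 = 14 days is an upper figure.
- Assumed: one compartment, linear kinetics, full doses at nominal times, equal clearance in both paths. Placebo-arm patients are taken to enter the concentration summaries once they receive E6011.

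**Formula.** Trough = sum over earlier doses of 2^(−days since dose / half-life), in units of one dose's initial concentration.

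**Week 16, placebo arm, 14 days.** Extension has one dose, 28 days earlier: 2^(−2) = 0.25. Rescue has doses 28, 21 and 14 days earlier: 0.25 + 0.354 + 0.50 = 1.104. Ratio 1.104/0.25 = 4.4.

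**Week 16, E6011 arm.** What remains of the seven induction doses adds 0.252 to both paths: 0.502 against 1.355, ratio 2.7.

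| Half-life 14 days | Extension | Rescue | Ratio |
|---|---|---|---|
| E6011 arm, Week 16 | 0.502 | 1.355 | 2.70 |
| E6011 arm, Week 20 | 0.375 | 1.089 | 2.90 |
| E6011 arm, Week 24 | 0.344 | 1.022 | 2.97 |
| Placebo arm, Week 16 | 0.250 | 1.104 | 4.41 |
| Placebo arm, Week 20 | 0.312 | 1.026 | 3.28 |
| Placebo arm, Week 24 | 0.328 | 1.006 | 3.07 |

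As a check, the steady-state ratio of two-weekly to four-weekly troughs is 1 + 2^(14/half-life), which is 3.00 at 14 days.

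**Sensitivity to half-life, Weeks 16 to 24, both arms.** 12 days: 3.1 to 4.7. 10 days: 3.6 to 5.3. 7 days: 5.0 to 7.0. Above the implied maximum, 16 days gives 2.5 to 4.2 and 21 days gives 2.1 to 3.9.

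**Effect on the pooled mean.** With an assumed half of each arm in each path, the pooled mean is 1.9 to 2.7 times the extension trough and 0.61 to 0.69 of the rescue trough. At Week 16 in the E6011 arm, for example, (0.502 + 1.355)/2 = 0.929, and 0.929/0.502 = 1.85.

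**How long it lasts.** Rescue patients who continue are dosed every four weeks from Week 24, so each path's next trough is (previous trough + 1) × 0.25. In the E6011 arm, Week 28 is 0.506 against 0.336 (ratio 1.5) and Week 32 is 0.376 against 0.334 (ratio 1.1). The placebo arm gives the same rounded ratios.

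**The case against.** The strongest reply is the deferral in SAP section 6. The separate PK plan may already split by path, so a reader who infers that the trial will nowhere report exposure by regimen goes further than the documents allow. That stands. It does not remove the point, because this SAP itself specifies the tables, mean profiles and PK-PD plots.

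Second, individual concentrations, actual sampling times and one plot per patient are all planned (SAP 4.8 and 10). With 25 enrolled (protocol 9.7.2) and a mainly descriptive analysis, each regimen can be read from these outputs, and no decision rule uses the pooled means. This limits the harm but does not correct the means, SDs or mean profiles.

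Third, the fold-difference is a model result. If, as an extreme, rescue patients had a 7-day half-life and responders 14 days, both steady-state troughs would be 0.25/0.75 = 0.33. It cannot be stated as fact that non-responders will have the higher troughs.

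Two wider readings are tempting.
- One is that a planned concentration-against-CDAI plot will show higher exposure with worse disease. SAP 6.10.5 plots concentration, CDAI, PRO2 and SES-CD each against a PD biomarker, so that plot is not clearly planned, and it does not say which visits enter. Total FKN is sampled only to Week 12. Calprotectin and CRP do continue in both paths, so for them the artefact is possible but not shown. Presenting the overlays by dose would not separate the paths, since both receive 10 mg/kg.
- The other is that the later CDAI and PRO2 tables share the fault. The trough calculation says nothing about them, and SAP 6.8.2 names visits only to Week 12.

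**Conclusion.** The point holds for E6011 concentrations at Weeks 16, 20 and 24, with a smaller residue at Week 28. Followed as written, this SAP averages two dosing intervals within an induction arm; its race split does not separate them. The size is 2.7 to 3.0-fold in the E6011 arm and 3.1 to 4.4-fold in the placebo arm, given linear one-compartment kinetics, equal clearance and a 14-day half-life. It also needs both paths represented in the arm: if nearly everyone takes one path, the mean is close to that regimen. It is a reporting fault worth correcting before the entire-period analysis and has no bearing on the Week 12 primary analysis.

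**What to change.** In SAP 4.8, 6.10.2 and 10, present E6011 concentration summaries and mean profiles for Weeks 16 to 28 by induction arm and Week 12 path (extension or rescue). Show n and the individual values, and drop the further race split where cells are very small.

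In SAP 6.10.5, split or mark by path any overlay or scatter plot that uses post-Week 12 concentrations with calprotectin or CRP.

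State in SAP section 6 how these outputs relate to the separate PK plan, and make the two agree.

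The cost is one derived variable and some wording, with no new data and no change to conduct. The drawback is small cells: 25/4 is about 6 per arm and path, and 25/8 is about 3 if race is kept, before dropout and assuming an even split.
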